Table 6: Transplantation Phase Study Procedures for Recipients of Kidneys from HCV RNA-Negative/HCV Antibody-Positive Donors in Arm 2A

Week of or after Kidney Transplant	Day of or after Kidney Transplant*	Study Visit	Research Visit Activities			Research labs					G/P	Standard of Care						
			Assess Adverse Events ⁶	Current Medications	Confirm donor-recipient pair meet trial criteria ¹	HCV Antibody	Urine Prot./Creat. Ratio	HCV RNA ²	Archive blood/sample	DAA resistance sample		Donor blood sample ³	Study drugs dispensed	HCV RNA	Vitals & PE	Clinical Chemistry	Hematology	Tacrolimus Level ⁴
0	Peri-transplant visit	V1	✓	✓	✓						✓							
1	7 ± 2 day	V2	✓	✓				✓										
4	28 ± 7 days	V3	✓	✓			✓		✓			✓						
8	56 ± 7 days	V4	✓	✓					✓									
24 ⁵	168 ± 14 days	V5	✓	✓		✓	✓	✓	✓									
End of study Visit	1 year ± 28 days	V6	✓	✓		✓	✓		✓									
HCV RNA Detected			✓	✓			✓	✓	✓			✓		✓	✓			

1 Includes evaluation of blood type and HLA compatibility

2 First quantifiable HCV RNA should trigger the reactive G/P treatment; First “detectable” but not quantifiable HCV RNA requires a follow-up HCV RNA blood draw and test for confirmation within 1 week of results of 1st “detectable” but not quantifiable RNA result; the second (confirmatory) positive e.g., “detectable or quantifiable” HCV RNA should trigger the reactive G/P treatment

3 If available. Lack of availability of donor blood sample will not preclude donor eligibility. Donor blood sample will be frozen and will be shipped to clinical coordinating center laboratory at MGH as needed for DAA resistance testing. See section 3.5.1.1

4 Includes Tacrolimus level and/or other utilized immunosuppressant that requires therapeutic drug monitoring

5 If subject visit 6 ±28 days would be equal to or exceeds 365 days from date of

enrollment, then visit 5 will be also the end of study visit.

6 Assess for clinical outcomes, including sclerosing cholestatic hepatitis, and extrahepatic manifestations of HCV at Visits 2-6 if treated with G/P.

7 4 Archived plasma samples (required) and PBMC (optional and restricted to sites with collection capability at weeks 8, 24, and end of study) samples are shipped to the clinical coordinating center at Massachusetts General Hospital, see section 5.3.1.1

5.1.8 “Reactive G/P Treatment Phase” -- only for subjects who experience HCV infection after transplantation of a kidney from a HCV RNA-negative/HCV antibody-positive donor in Arm 2A

Reactive Visit 1 (within 2 weeks of positive HCV RNA)

Reactive Visit 1 should occur approximately within 2 weeks after the subject’s first positive HCV RNA. The first quantifiable HCV RNA should trigger the reactive G/P treatment. If the first positive HCV RNA is “detectable” but not quantifiable, then, to confirm the result, a follow-up HCV RNA blood draw is required as soon as possible. A second (confirmatory) positive, e.g., “detectable or quantifiable”, HCV RNA should trigger the reactive G/P treatment. The subject will arrive at the study site outpatient clinic. The following standard of care procedures and activities will be performed:

- Assess for Adverse Events, and clinical outcomes, including: death, graft failure, acute allograft rejection, delayed graft function ALT elevation > 5x ULN, SAEs, sclerosing cholestatic hepatitis, and extrahepatic manifestations of HCV.
- Obtain medication data
- Physical examination, vital signs
- Phlebotomy
- Where applicable, pregnancy testing must be performed prior to starting G/P, and G/P should not be started when pregnancy test is positive
- Schedule appointments for follow-up visits
- Dispense G/P

The following information of standard-of care follow up visits after reactive Visit 1 will be collected retrospectively, abstracted from subject records and recorded in study eCRFs: Any SAE and relatedness of SAE to G/P during G/P treatment from the 1st dose of G/P to 30 days post last dose of G/P treatment; any G/P treatment emergent laboratory abnormality \geq Grade 3 until 2 days post last day of G/P treatment; any early discontinuation of G/P.; HCV plasma RNA before start of G/P treatment and post G/P treatment week 12; reason for not achieving SVR12 if applicable.

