Subjects who are transplanted with kidneys from HCV RNA-positive donors in Arm 1 will be followed for 1 year after the date of transplantation to evaluate SVR12, SVR24, safety, death, graft failure, acute allograft rejection, delayed graft function, ALT elevation >5 times the upper limit of normal, eGFR and proteinuria. Specifically, scheduled in-person visits for subjects who received organs from HCV RNA-positive donors in Arm 1 and receive G/P treatment will consist of day of transplant, Day 1 of G/P treatment, weeks 1, 2, 4, and 8 (planned end of treatment visit) after starting G/P. Additional scheduled visits will take place at Post Treatment Week 4, Post Treatment Week 12, Post Treatment Week 24 (e.g., post G/P treatment visits) to evaluate SVR4, SVR12 and SVR24 and 1 year post transplant. The post-transplant study visit schedule for MYTHIC has been designed such that these visits should take place on the same days as standard of care clinical visits. For subjects in Arm 1 study-objective pertinent data will be collected while awaiting a transplant (ie, SAEs, hospitalizations, delisting from waitlist, death), and post-transplant (ie, death, graft failure, acute allograft rejection, delayed graft function, eGFR, proteinuria, ALT elevation >5 times the upper limit of normal, and SAEs). Subjects who experience virologic failure in

Arm 1 will be evaluated for the emergence/persistence of DAA-resistant viral variants, and suitable retreatment will be offered.

Study visits in Arm 2A will take place at weeks 1, 4, 8, 12, and 24 weeks after transplantation. Safety, graft survival, mortality, allograft rejection, and results of HCV RNA testing will be captured for a period of 24 weeks post-transplant. Study-objective pertinent data will be collected while awaiting a transplant (i.e., SAEs, delisting from waitlist, death), and post-transplant (i.e., death, graft failure, acute allograft rejection, delayed graft function, eGFR, proteinuria, ALT elevation >5 times the upper limit of normal, and SAEs). For subjects of Arm 1 and Arm 2A who become HCV infected, we will collect additional clinical outcomes of sclerosing cholestatic hepatitis and extrahepatic manifestations of HCV.

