Efficacy and safety outcomes assessments recorded in the medical record as part of the subject's standard clinical management and follow up will be submitted using electronic CRFs where available in the medical record, except for protocol defined central laboratory assessment collection, drug dispensation and accountability, and required monthly medical record source record verification/submission. The central laboratory will be at MGH.

The schedule of procedures for the study regarding the treatment of HCV infection for recipients of HCV RNA-positive kidneys in Arm 1 ([Table 5](#)) is more intense but principally based on the AASLD guidelines²⁶ for the treatment of HCV, which recommends:

1) Baseline: hepatic fibrosis assessment, drug-drug interaction assessment, hepatitis B serologies (HBs Ag, anti-HBc, anti-HBs, reflex HBV DNA if anti-HBc-positive),

CBC/platelets, hepatic function panel, and estimated glomerular filtration rate (eGFR, done in this study using the MDRD equation);

2) On treatment monitoring: HCV RNA and routine CBC/platelets, hepatic panel and eGFR) are recommended at week 4 and as clinically indicated;

3) Post-treatment monitoring: HCV RNA and routine labs are recommended at 4 and 12 weeks post-treatment.

In Arm 1, G/P dosing in Arm 1, treatment/side effect management, and duration will be recorded in the study CRFs by the site PI and or clinical provider designee and managed according to the AASLD guidelines, center standard of care, with additional assessments required by the protocol according to the Study Activities table ([Table 5](#)).

The schedule of procedures regarding kidney transplantation activities is based on the local center's practice for kidney transplant care.

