All subjects who received at least one dose of study drug will be monitored during the post-transplantation period for safety, HCV RNA, and the emergence and persistence of resistance-associated viral substitutions for an additional 12 and 24 weeks following the last dose of G/P. For recipients of HCV RNA-positive transplants in Arm 1, a 1-year post kidney transplant visit is included to assess for graft function and survival, eGFR and proteinuria, and donor specific antibody (abstracted from the center's medical records), as applicable per the center's standard of care.

Appropriate information from original clinic notes, telephone notes, locally available safety labs/evaluations and/or diagnostic tests, or health screenings collected during the post-HCV treatment period will be abstracted at the clinical sites to identify and report adverse events, vital signs, physical examinations, concomitant medications, HCV RNA, HCV resistance, and clinical laboratory tests that were collected as part of standard of care practice.

The Post-Treatment Period will begin the day following the last dose of study drug treatment.

Subjects who prematurely discontinue treatment should return to the site for a Post-Treatment Discontinuation Visit as outlined in Tables [5](#) and [7](#) and will be followed for all post-treatment safety, HCV RNA, and resistance-associated substitutions according to the post treatment period schedule.

5.1.6.1 Post-treatment visits for subjects who receive an HCV RNA-positive kidney in Arm 1

Visit 9: Telephone encounter or in person visit (4 week after end of G/P treatment)

Visit 9 should occur 4 weeks after end of G/P treatment ± 7 days. Note that this visit can be performed as an in-person visit to the study site, if there is a standard of care post-transplant visit on the same date.

The following research procedures and activities will be performed

- Assess for Transplant-related, HCV-related, and study drug related Adverse Events, including clinical outcomes (same as described in Visit 3)
- Obtain medication data
- Confirm follow-up visits

Visit 10: (12 weeks after end of G/P treatment)

Visit 10 should occur 12 weeks after end of G/P treatment ± 14 days. If possible, it should immediately follow the subject's regularly scheduled post-transplant follow-up visit at the study site and will provide an opportunity to assess SVR12.

The following research procedures and activities will be performed:

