Day 1 of G/P treatment	V3	✓	✓								✓	✓	✓	✓	✓				
Treatment week 1 ±3 days	V4	✓	✓		✓			✓					✓	✓	✓				
Treatment week 2 ±3 days	V5 T5	✓	✓		✓														
Treatment week 4 ±3 days	V6	✓	✓		✓	✓		✓			✓	✓	✓	✓	✓	✓			
Treatment week 6 ±3 days ¹⁰	T7	✓	✓		✓														
Treatment week 8 ±7 days (EOT)	V8	✓	✓		✓			✓			✓		✓	✓	✓				
Post treatment week 4 ±7 days	V9 T9	✓	✓																
Post treatment week 12 ±14 days	V10	✓	✓					✓	✓										
Post treatment week 24 ±28 days	V11	✓	✓					✓	✓				✓	✓	✓				
1 year Post transplant ±28 days; End of study ¹¹	V12	✓	✓					✓	✓				✓	✓	✓				
G/P treatment failure		✓						✓	✓	✓									
Premature discontinuation		✓						✓	✓	✓			✓	✓	✓				

1 Visit types: V - in person visit to site; L - Lab visit; T - Telephone encounter

2 Includes evaluation of blood type and HLA compatibility

3 HCV RNA testing at V2, V4, V8, and V10 and V11 are study paid labs. HCV RNA testing at visit 6 is billed as SOC. All HCV RNA testing is done at local laboratory by a CLIA certified laboratory and with an FDA approved test.

4 Archived plasma samples (required) and PBMC (optional at Visits 8, 10, and 12) samples are shipped to the clinical coordinating center at Massachusetts General Hospital, see section 5.3.1.1

5 Lack of availability of donor blood sample will not preclude donor eligibility or transplant. HCV genotype is determined from the donor blood sample at local laboratory; Another portion of the donor sample is frozen for storage and potential testing for DAA resistance as needed. See section

5.3.1.1

6 If visit 2 and visit 3 are on the same day or within 14 days of each other only 1 serum pregnancy test need to be obtained. Visit 6 and Visit 8 pregnancy tests can be urine tests. Additional pregnancy tests not billed to the study are obtained as per transplant center standard of care.

7 Vitals and physical exam will be conducted and documented as per standard of care at transplant center

8 Liver function tests (ALT, AST, Alk Phos., total bilirubin) will be ordered as a study lab if not standard of care as part of clinical chemistry labs at the local transplant center. See table 8 for clinical chemistry labs and hematology labs.

9 Includes Tacrolimus level and/or other utilized immunosuppressant that requires therapeutic drug monitoring as per transplant center standard of care;

10 Telephone call will be performed between clinic visits at treatment week 6 to assess subject adherence to G/P treatment.

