8.1 Statistical and Analytical Plans

The data analysis will be generated using SAS version 9.4 or higher for windows and/or STATA software version 14.0 or higher (StataCorp LP, College Station, TX). SAS Institute Inc. SAS and all other SAS Institute Inc. product or service names are registered trademarks or trademarks of SAS Institute Inc., Cary, NC, USA. All statistical tests (if applicable) and confidence intervals will be two-sided with an alpha level of 0.05.

Descriptive statistics will be provided, such as the number of observations (N), mean, and standard deviation (SD) for continuous variables and counts and percentages for discrete variables.

The efficacy and safety of the “reactive” G/P treatment of patients who become HCV RNA-positive after receiving a kidney from a study eligible HCV RNA-negative/HCV Ab-positive donor in Arm 2A are not an objective of this study, and they are not included in assessments of efficacy or safety described below. The time to transplant and clinical outcomes and data post-transplant from patients in Arm 2A are included in those secondary endpoints.

The primary analysis will occur after all recipients of HCV RNA-positive kidneys in Arm 1 have completed post-treatment week 12 visit (corresponding to SVR₁₂ data collection) or prematurely discontinued study. The primary analysis of SVR₁₂ will be performed on the intention-to-treat (ITT) population defined as all enrolled subjects who received a study eligible HCV RNA-positive kidney and received at least one dose of G/P according to actual treatment received (Arm 1).

No data will be imputed for any efficacy or safety analysis except for analyses of SVR endpoints (HCV RNA data). HCV RNA values will be selected for the analyses of all SVR endpoints (e.g., SVR₄ and SVR₁₂, SVR₂₄) based on defined visit windows. A backward imputation method will be used to impute missing responses for SVR analyses. Additional details of analyses to be performed will be specified in the Statistical Analysis Plan.

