8.1.2.1 Primary Efficacy Endpoint

The primary efficacy endpoints is the proportion of ITT subjects who achieved SVR₁₂ (HCV RNA < LLOQ 12 weeks after the last actual dose of study drug).

The number and percentage of subject achieving SVR₁₂ will be summarized along with a two-sided 95% confidence interval calculated using Wilson's score method. A summary of reasons for SVR₁₂ non-response (e.g., on-treatment virologic failure, relapse, other) will be provided.

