8.1.2.2 Secondary Efficacy Endpoints

The secondary efficacy endpoints to be summarized for all ITT subjects who are:

- the number and percentage of subjects with on-treatment virologic failure (confirmed increase of $> 1 \log_{10}$ IU/mL above nadir during treatment, confirmed HCV RNA ≥ 100 IU/mL after HCV RNA $<$ LLOQ during treatment, or HCV RNA \geq LLOQ at the end of treatment with at least 6 weeks of treatment);
- the number and percentage of subjects with post-treatment relapse (defined as confirmed HCV RNA \geq LLOQ between end of treatment and 12 weeks after the last dose of study drug among subjects who completed treatment as planned with HCV RNA $<$ LLOQ at the end of treatment, excluding subjects with reinfection).

For the analysis of relapse, completion of treatment is defined as any subject with study drug duration of 49 days or greater for 8-week treatment.

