8.1.2.5 Additional Efficacy Endpoints

The following additional efficacy endpoints will be summarized for the ITT population:

- The percentage of subjects with HCV RNA < LLOQ at each post-baseline visit in the Treatment Period (using data as observed);
- The percentage of subjects with SVR4;
- The percentage of subjects with SVR24 and the concordance between SVR12 and SVR24

In the above analyses for SVR, the percentage of subjects and a two-sided 95% Wilson score interval will be summarized.

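### SVR4 is a planned endpoint, but no HCV RNA test is scheduled at post-treatment week 4, so for recipients tested only per schedule it largely repeats SVR12

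*Protocol*

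**What the plan says.** **SVR4 is planned.** Protocol 5.1 describes the post-treatment week 4, 12 and 24 visits as being there "e.g., post G/P treatment visits) to evaluate SVR4, SVR12 and SVR24". Section 8.1 names SVR4 among the endpoints to be taken from visit windows. Section 8.1.2.5 lists "The percentage of subjects with SVR4" for the ITT population, with a 95% Wilson interval.

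**The week-4 sample is not scheduled.** Footnote 3 of Table 5 says "HCV RNA testing at V2, V4, V8, and V10 and V11 are study paid labs" and adds Visit 6 as a usual-care test. The V9/T9 row is ticked for adverse events and medications only. Section 5.1.6.1 heads the contact "Visit 9: Telephone encounter or in person visit (4 week after end of G/P treatment" and lists no phlebotomy, whereas Visits 10 and 11 both list it. The opening of 5.1.6 speaks of HCV RNA monitoring at 12 and 24 weeks, with no mention of week 4.

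**The guidance behind the schedule includes week 4.** Section 5.1.5 says the Arm 1 schedule builds on, and goes beyond, the AASLD guidance. It reports that guidance as follows: "HCV RNA and routine labs are recommended at 4 and 12 weeks post-treatment".

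**Missing values.** Section 8.1 states: "A backward imputation method will be used to impute missing responses for SVR analyses". It leaves further detail to the SAP. The SAP summary has rows for SVR12, virologic failure and relapse. It has no SVR4 row, no visit windows and no imputation rule.

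**The concern.** The plan promises an estimate for which it schedules no measurement. Followed as written, it would report an SVR4 percentage with its own confidence interval that, for anyone tested only per schedule, comes from a sample taken at week 12 or later. A reader of the results would take it as separate evidence of early response.

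The same gap touches relapse, which is a secondary endpoint. Section 8.1.2.2 requires confirmed HCV RNA at or above "LLOQ between end of treatment and 12 weeks after the last dose of study drug". Once treatment has ended, the first routine look inside that interval is Visit 10, at its far end. Recipients who relapse are promised retreatment (5.5.1.1), so a late first look delays that treatment. It also makes it more likely that someone who leaves before Visit 10 has no result showing why. Section 8.1.2.1 plans a summary of reasons for "non-response (e.g., on-treatment virologic failure, relapse, other", and such a case would tend to be classed as other.

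**Working it through.** The plan states no figure to reproduce. The check is a comparison of visit windows, followed by simple arithmetic on lag and expected counts.

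**1. Sampling windows, in days after the last dose of a 56-day course** (from 5.1.5.1, 5.1.6.1 and Table 5)

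| Visit | Nominal day and window | Range | HCV RNA scheduled? |
|---|---|---|---|
| V8 (end of treatment) | 0 ± 7 | −7 to 7 | Yes |
| V9 (post-treatment week 4) | 28 ± 7 | 21 to 35 | No |
| V10 (post-treatment week 12) | 84 ± 14 | 70 to 98 | Yes |
| V11 (post-treatment week 24) | 168 ± 28 | 140 to 196 | Yes |

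No routine draw falls in days 21 to 35. The next one opens 70 − 35 = 35 days after that window closes, and is nominally 84 − 28 = 56 days after Visit 9. Carrying the next available value backward therefore fills SVR4 from V10, or from V11 if V10 is missed. If backward imputation is not applied, SVR4 is simply missing for these recipients.

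**2. Time from transplant to the first routine relapse sample**, with G/P started on day 3, the target in 5.1

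- As scheduled: 3/7 + 8 + 12 = 20.4 weeks. With the ±14-day window, 18.4 to 22.4.
- With a Visit 9 draw: 3/7 + 8 + 4 = 12.4 weeks. With the ±7-day window, 11.4 to 13.4.

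The difference is 8 weeks. A later G/P start moves both figures by the same amount. Over the stretch from last dose to V10, the longest nominal gap without a test falls from 84 to 56 days.

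**3. Expected counts among 30 Arm 1 recipients**

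Let p be the relapse probability and q the share of relapses already detectable at week 4. Section 5.5.8.1 gives 22 virologic failures among 2258 treated subjects, so p = 22/2258 = 0.97%. That count covers all virologic failure in chronic infection, so using it for relapse here is an assumption. The documents give no value for q, and none for a higher p. Both are shown as assumed ranges.

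- Expected relapses = 30p
- Found 8 weeks sooner = 30pq
- Recipients whose measured SVR4 would differ from SVR12 = 30p(1 − q)

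| p | 30p | Found sooner, q = 25/50/100% | SVR4 differs from SVR12, q = 25/50/100% |
|---|---|---|---|
| 0.97% (documented) | 0.29 | 0.07 / 0.15 / 0.29 | 0.22 / 0.15 / 0 |
| 5% (assumed) | 1.5 | 0.38 / 0.75 / 1.5 | 1.13 / 0.75 / 0 |
| 10% (assumed) | 3.0 | 0.75 / 1.5 / 3.0 | 2.25 / 1.5 / 0 |

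At the documented rate, every entry is a fraction of one recipient.

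**The case against.** The best defence is that usual care may supply the sample. Section 5.1.5 has Arm 1 treatment managed under the guidance and centre practice, with protocol assessments on top. Section 5.1.6 has sites abstract usual-care HCV RNA from the post-treatment period, and footnote 3 already relies on usual care at Visit 6. This stands in part: some recipients may well have a week-4 value. But where the protocol counts on a usual-care HCV RNA it says so, and for Visit 9 it does not.

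Four stronger readings are tempting, and the documents do not support them.

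- **SVR4 equals SVR12 by construction.** That would require that no usual-care value exists and that the imputation rule is fully specified. Section 8.1 names the method without defining it, and the SAP summary does not fill this in. Back-filling from V10 is the plain reading, not a written rule.
- **No sample can exist between the last dose and V10.** The V8 draw may fall up to about 7 days after the last dose, and Table 5 has event-triggered HCV RNA rows for treatment failure and premature discontinuation. The 20.4 weeks describes routine post-treatment sampling only.
- **A single positive at Visit 9 would settle relapse.** Section 8.1.2.2 asks for a confirmed value, so one draw without a repeat would not reclassify a recipient who then leaves.
- **The stopping rule in 5.4.2 is undermined.** At a 0.97% failure rate the rule is met with probability about 0.01%. Any gain from earlier results depends on an accrual speed and relapse rate that the documents do not give.

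It is also fair to say that SVR4 is neither primary nor secondary, and that deleting it would remove the contradiction.

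**Conclusion.** The inconsistency is real. It is not an artefact of a damaged table, because the V9/T9 row, footnote 3 and the Visit 9 list agree with one another and conflict with 5.1, 8.1 and 8.1.2.5. For recipients tested only per schedule, SVR4 largely repeats SVR12, and routine detection of relapse comes about 8 weeks later than it need.

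The effect is modest. The primary SVR12, its Visit 10 sample and its interval are untouched, and about 0.3 relapses are expected among 30 recipients at the documented rate. The conclusion rests on G/P starting on day 3, a full 56-day course, the plain reading of backward imputation, and no usual-care week-4 result. It deserves correction because the plan contradicts itself on a reported endpoint and the remedy is cheap.

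**What to change.** Preferred: take HCV RNA at Visit 9. This needs consistent edits in these places:

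- Table 5: tick HCV RNA in the post-treatment week 4 row, and add V9 to footnote 3.
- Section 5.1.6.1: add the draw to the Visit 9 procedure list.
- Visit 9 heading and its V9/T9 code: change to in person, or to a lab visit plus a call (footnote 1 already defines a lab visit type).
- Opening of 5.1.6: add week 4 to the monitoring times.
- New instruction: repeat promptly any HCV RNA at or above LLOQ, so that it can count as confirmed relapse under 8.1.2.2.

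The cost is about 30 local HCV RNA tests plus the occasional repeat, and Visit 9 can no longer be by telephone only. A negative week-4 result does not exclude later relapse, so week 12 stays the primary time point.

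Alternative: delete SVR4 from 5.1, 8.1 and 8.1.2.5. That removes the contradiction at no cost but leaves the 20.4-week lag.
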